9.6. Pharmacogenomic Evaluations

There are 2 parts to the pharmacogenomic component of this study.

Analysis Related to the Study (Part 1)

Part 1 of pharmacogenomic research allows for the analysis of genes that may be relevant to help to better understand canagliflozin, or T2DM or obesity. Candidate genes will only be genotyped, if it is hypothesized that this may help resolve issues with the clinical data. Analyses may involve the analysis of known candidate genes or the analysis of genetic variants throughout the genome (genome-wide association analysis), both in relation to canagliflozin, or T2DM or obesity (provided in Attachment 8). Genotyping of any of these candidate genes would be performed on identifiable samples.

Additional genes may be analyzed on identifiable samples if these genes are hypothesized to be relevant to canagliflozin, or T2DM or obesity between the time that the clinical protocol has been issued and the samples have been made nonidentifiable.

DNA Storage for Future Research (Part 2)

Part 2 of the pharmacogenomic research allows for the storage of DNA samples for future genetic research related to canagliflozin or the indication(s) for which it is developed. Stored DNA samples and relevant clinical data will be made nonidentifiable after the Clinical Study Report has been issued. This involves removing personal identifiers and replacing the study subject identifier with a new number to limit the possibility of linking genetic data to a subject's identity.

Subjects will be given the option to participate in Part 1 only, Part 2 only, both parts, or neither part of the pharmacogenomic component of this study (where local regulations permit).

9.7. Exploratory Evaluations

A set of fasting plasma, serum, and urine samples will be collected (where local regulations permit) at the time points specified in the Time and Events Schedule for the following:

- exploratory analysis that may be done to provide insight into the actions of canagliflozin or assist in understanding of adverse events possibly associated with the compound. Samples may also be used for future exploratory research to improve understanding of the pathophysiology of T2DM or obesity or to assess other pharmacodynamic effects of canagliflozin, and
- to develop biomarkers that may provide further understanding regarding the risk of development of diabetes-related complications.

This exploratory evaluation is optional and will only be performed in subjects who give informed consent for this specific component of the study.

9.8. Medical Resource Utilization

Subjects will be requested to collect information in a protocol-specified diary on information related to their utilization of medical resources (see [Attachment 9](#)). This MRU data from the subject diaries will then be documented in the eCRF by the investigator and study research staff for all subjects at each visit throughout the study. Protocol-mandated procedures, tests, and encounters are excluded.

The data collected may be used to conduct exploratory economic analyses.

No cost data will be collected in this study.

10. SUBJECT COMPLETION/WITHDRAWAL

10.1. Completion

A subject will be considered to have completed the study if he or she has experienced a clinical endpoint that precludes further study (eg, early mortality due to CV event) or when the study ends. Note that occurrence of a nonfatal event in the CV composite endpoint (ie, nonfatal MI, nonfatal stroke) is not a study withdrawal criteria. Subjects with these events should be continued in the study, on study drug, unless they meet a study withdrawal criterion (see [Section 10.2, Withdrawal From the Study](#)). Subjects who prematurely discontinue study treatment for any reason before completion of the double-blind treatment phase will not be considered to have completed the study.

10.2. Withdrawal From Study Drug

A subject will be withdrawn from the study drug for any of the following reasons:

- Lost to follow-up
- Withdrawal of consent (subject withdrew consent for treatment and refuses any further follow-up)
- Subject is persistently in poor compliance with study treatment or procedures
- The investigator believes that for safety or tolerability reasons (eg, an adverse event) it is in the best interest of the subject to stop treatment
- The subject becomes pregnant (study therapy should be immediately discontinued based upon a positive urinary hCG, and permanently discontinued if confirmed by a serum β -hCG test)
- The subject's eGFR is <15 mL/min/1.73m² (as reported by the central laboratory).

Note: the central laboratory will alert the investigator for eGFR values <15 mL/min/1.73m². A repeat determination should be performed within 2 weeks, and study treatment discontinued if the repeat eGFR is <15 mL/min/1.73m² (unless a reversible cause is identified [eg, short-term illness or transient volume depletion] in

which case an additional repeat determination can be performed after resolution of the short-term illness).

- Subject requires dialysis or renal transplantation
- Subject has liver function test abnormalities meeting criteria for permanent discontinuation of study drug as outlined in [Attachment 7](#)
- The investigator formally unblinds the subject's treatment allocation
- Subject initiates disallowed therapy (refer to Section 8, Prestudy and Concomitant Therapy)
- The subject experiences a serious adverse event of biochemically-confirmed (eg, pH, serum ketones, anion gap) DKA.

The end-of-treatment evaluations should be performed as soon as possible after stopping the study drug (see Section 9.1.4, End-of-Treatment/Early Withdrawal, and the Time and Events Schedule that follows the Synopsis for procedures to be performed). For posttreatment follow-up contacts, refer to Section 9.1.5, Posttreatment Phase (Follow-up).

Subjects who decide to withdraw from double-blind study drug must be interviewed by the investigator so as to determine if a specific reason for withdrawal can be identified. If the subject elects to withdraw due to an adverse event, the event should be recorded as the reason for withdrawal, even if the investigator's assessment is that the adverse event would not require study drug withdrawal.

When a subject withdraws from double-blind study drug before completing the study, the reason for withdrawal is to be documented in the eCRF and in the source documentation. Study drug assigned to the withdrawn subject may not be assigned to another subject. Subjects who withdraw will not be replaced.

A subject who elects to withdraw consent for the biomarker specimen collections will not have further collections made after withdrawing consent, and has the following options:

- to allow the previously collected specimens to remain for biomarker analysis, or
- to request that the previously collected specimens be destroyed.

A subject who withdraws from the main part of the study will have the following options regarding pharmacogenomic research:

- The DNA extracted from the subject's blood will be retained and used in accordance with the subject's original pharmacogenomic informed consent.
- The subject may withdraw consent for pharmacogenomic research, in which case the DNA sample will be destroyed and no further testing will take place. To initiate the sample destruction process, the investigator must notify the sponsor site contact to request sample destruction. The sponsor site contact will, in turn, contact the pharmacogenomics representative to execute sample destruction. If requested, the

investigator will receive written confirmation from the sponsor that the sample has been destroyed.

Withdrawal from Pharmacogenomic Research Only

The subject may withdraw consent for pharmacogenomic research while remaining in the clinical study. In such a case, any DNA extracted from the subject's blood will be destroyed. The sample destruction process will proceed as described above. However, all samples will be made nonidentifiable after the Clinical Study Report is issued and thereafter cannot be identified for destruction. If the sample has already undergone conversion to the nonidentifiable format, the sponsor will notify the investigator in writing.

10.3. Reinstitution of Subjects Who Have Prematurely Discontinued Double-Blind Study Drug to Active Status

Subjects for whom study drug is interrupted as a result of an adverse event, a life event (eg, temporary relocation to care for an ill family member), or other unforeseen circumstance may return to active status (ie, re-start double-blind study drug) in the study at the discretion of the investigator, with concurrence from the sponsor's medical monitor, even if previously withdrawn from the study or off study drug for up to 90 days. Subjects off study drug for more than 90 days, or subjects who meet the conditions that require withdrawal (eg, unblinding), should not be returned to active status. If the subject had previously withdrawn consent but decides to retract that withdrawal, the subject will be reconsented. The investigator will be responsible for making all required notifications to the IRB or Ethical Committee.

10.4. Measures to Re-establish Contact in Subjects Lost to Follow-up

If a subject is lost to follow-up, **all possible efforts must be made by the study site personnel to contact the subject and to determine endpoint status and the reason for discontinuation/withdrawal.** The measures taken to follow-up must be documented. The informed consent form will stipulate that even if a subject decides to discontinue double-blind study drug, he/she will agree to be contacted periodically by the investigator to assess his/her endpoint status (refer to the Posttreatment Time and Events Schedule for subjects that prematurely discontinue double-blind study drug). Furthermore, the subject will be asked to agree to grant permission for the investigator to consult family members, the subject's physicians and medical records, or public records, including the use of locator agencies as permitted by local law, to determine the subject's endpoint status, in the event the subject is not reachable by conventional means (eg, office visit, telephone, email, or certified mail). The subject is informed that if the site of the study doctor closes, and the study doctor cannot reach the subject to inform him/her, the contact information will be transferred to another site where a new study doctor will consult with family members, the subject's physicians and medical records, or public records, including the use of locator agencies as permitted by local law, to determine the subject's endpoint status.

11. STATISTICAL METHODS

Statistical analysis will be done by the sponsor or under the authority of the sponsor. A general description of the statistical methods to be used to analyze the efficacy and safety data is outlined below. Specific details will be provided in the SAP.

11.1. Analysis Sets

The ITT analysis set includes all subjects who are randomly assigned to a treatment group. The assessment of the primary objective will be based upon this analysis set. The primary CV analysis will be based on the time to the first occurrence of any component of the CV composite endpoint.

The modified intent-to-treat (mITT) analysis set includes randomized subjects who receive at least one dose of study drug and their data occurring between first dose and last dose plus 30 days.

The alignment of the analysis of the secondary endpoints with the ITT and mITT analysis sets will be detailed in the study SAP.

11.2. Handling of Dose in Analysis

The primary comparison, to assess CV risk reduction, will be between canagliflozin (100 and 300 mg groups combined) versus placebo. Additionally, the HR and its 2-sided 95% CIs versus placebo will be assessed for each dose of canagliflozin.

11.3. Sample Size Determination

The sample size for the recruitment of the initial 4,500 subjects was based upon having a sufficient number of participants to support, in concert with the other controlled clinical trials in the canagliflozin development program, a detailed pre-approval assessment of the safety and tolerability of canagliflozin. Data from this initial cohort were exported and integrated with data from other Phase 3 well-controlled studies to support a planned pre-approval meta-analysis to demonstrate that the upper bound of the 2-sided 95% CI for the CV HR of canagliflozin relative to control in composite endpoint events (MACE and hospitalized unstable angina) was <1.8 ; the current US regulatory requirements for filing. The FDA post-marketing requirements for canagliflozin demand a subsequent estimate of CV safety that will be performed on data from CANVAS and CANVAS-R, when sufficient events have occurred to demonstrate that the upper bound of the 95% CI HR is <1.3 based on MACE (excluding hospitalized unstable angina).

The assumed per annum event rate is 2.25% and the per annum dropout rate is 5%. With an enrollment period 1.5 years, 4,500 randomized subjects were projected to contribute sufficient CV events to support the pre-approval CV meta-analysis.

The original phased recruitment strategy allowed for an interim assessment of study feasibility to demonstrate the primary hypothesis of CV benefit using the results of the interim analysis. Results from the interim analysis (conducted after approximately 2 to

4 years from study initiation, eg, at approximately the time of US regulatory approval) were planned to be evaluated by a CV risk factor evaluation committee to assess the effect of canagliflozin on CV risk factors (to predict the likely effect of canagliflozin on CV events) and determine the point estimate for the HR for MACE. The data on the observed point estimate for the CV HR for MACE were to have been reviewed by the IDMC only and would not have been made more broadly available. Re-opening of enrollment was to have proceeded if the effects on the intermediate outcomes (ie, CV risk factors) as determined by appropriate models (to be prespecified before the interim analysis) that canagliflozin compared to placebo would result in an HR of 0.85 or less (for MACE) and if the observed HR (for MACE) is 0.95 or less. If recruitment did proceed, an additional 14,000 subjects would have been enrolled into Cohort B. However, for the reason outlined above (see Section 3), this second cohort will no longer be recruited.

Without the recruitment of the second cohort of 14,000 subjects, CANVAS study power is reduced from the originally planned 90% power to detect a HR of 0.85 or less. It is now projected that at the completion of the study there will be about 400 MACE events recorded within CANVAS, which will provide 33% power to detect a HR of 0.85 or less, 55% power to detect a HR of 0.80 or less, and 76% power to detect a HR of 0.75 or less using a 2-sided test with 0.05 alpha.

11.4. Safety Analyses

The safety analysis will be based on the mITT analysis set. The mITT analysis set includes all subjects who are randomly assigned to a treatment group and have received at least one dose of study drug and their data occurring between first dose and last dose plus 30 days. There will be no imputation for missing values for clinical laboratory test results or vital sign measurements in the analyses.

Safety and tolerability will be evaluated by summarizing and comparing the incidence of serious adverse events and adverse events of interest, discontinuation rate due to adverse events, clinically important changes in clinical laboratory tests, vital signs (pulse, blood pressure), and body weight between randomized groups. There will be no imputation for missing values for clinical laboratory test results or vital sign measurements in the analyses.

Adverse Events

The verbatim terms used in the eCRFs by investigators to identify adverse events will be coded using the Medical Dictionary for Regulatory Activities (MedDRA). All reported serious adverse events, adverse events resulting in study drug discontinuation, and adverse events of interest with onset during the treatment phase (ie, treatment-emergent adverse events) will be included in the analysis. For each adverse event, the percentage of subjects who experienced at least one occurrence of the given event will be summarized by treatment group. An adverse event will be considered to be a treatment-emergent

event if it occurs within 30 days of the last date of blinded study medication. The percentage of subjects with specific treatment-emergent adverse events will be summarized by severity and relationship to study drug, as classified by the investigators, for each treatment group.

Summaries, listings, datasets, or subject narratives may be provided, as appropriate, for those subjects who die, who discontinue treatment due to an adverse event, who experience a serious adverse event, or who experience an adverse event of interest.

Further analyses, described in the SAP for this study, will be conducted on the prespecified adverse events for which additional information is collected from the investigators (refer to Section 9.4, Safety Evaluations).

Clinical Laboratory Tests

Laboratory data will be summarized by type of laboratory test. Normal reference ranges will be provided. Criteria for markedly abnormal laboratory values will be prespecified in the SAP. The percentage of subjects with markedly abnormal results will be summarized for each laboratory analyte. Descriptive statistics will be reported for each laboratory analyte at baseline and at each scheduled time point and for change from baseline.

Vital Signs

Descriptive statistics for pulse and sitting blood pressure (systolic and diastolic) values and changes from baseline will be summarized at each scheduled time point. The percentage of subjects with values beyond clinically important limits will be summarized.

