- ^a Following the run-in visit, there will be a single-blind, placebo run-in period, during which therapy for diabetes should remain stable and therapy for CV risk factors (eg, blood pressure, fasting lipids) will be optimized as needed, at the investigator's discretion. Subjects who fail protocol-specified screening criteria for study entry may be rescreened, at the discretion of the investigator as described in Section 4.5, Rescreening.
- ^b End-of-treatment/early withdrawal evaluations will be performed when the double-blind treatment phase of the study is ended or at the time the subject discontinues the double-blind study drug or is withdrawn from the study. Evaluations will be performed as soon as possible after stopping the study drug. Subjects who discontinue double-blind treatment for any reason will have a posttreatment follow-up contact and visits according to the Posttreatment Time and Events Schedule for the duration of the study, until completion of the study. It is the expectation that the investigator will make every effort to ascertain the vital status of all subjects at the end of the study, including using all reasonable means to contact the subject, family members, the subject's physicians and medical records, and the use of locator agencies and checking public records, as allowed by local law.
- ^c A telephone follow-up contact (or optional study visit, at the discretion of the investigator) will be conducted for all subjects approximately 30 days (and no more than 42 days) after the last dose of study drug. If a telephone contact or study visit is not possible, follow-up information may be collected via email or other electronic or non-electronic means.
- ^d After Week 65, on those occasions when the 13- 26-, and/or 52-week-interval visits overlap each other, the visit with the more comprehensive procedures will be followed.
- ^e Telephone contact (or an optional, unscheduled site visit, at the discretion of the investigator) will be made at Weeks 2, 4, and 9 to check the subject's status, including discussing the subject's diary entries and any CV events or adverse events. If a telephone contact or study visit is not possible, follow-up information may be collected via email or other electronic or non-electronic means.
- ^f See Section 16.2.3, Informed Consent, for details. The informed consent form must be signed before any study procedure is performed.

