1.1.2. Clinical Studies

Pharmacokinetics

Canagliflozin exhibits similar PK in healthy subjects and subjects with T2DM. The mean absolute oral bioavailability of canagliflozin was 65% following single-dose administration of the canagliflozin 300 mg tablet in healthy subjects. In healthy subjects (25 to 1,600 mg once-daily [QD]) and subjects with T2DM (50 mg to 300 mg QD and 300 mg twice-daily [BID]), after oral administration of single and multiple doses, mean canagliflozin $AUC_{0-\infty}$ increased in an approximately dose-proportional manner whereas mean maximum plasma concentration (C_{max}) increased in an approximately dose-proportional manner up to 1,200 mg. Following oral administration of canagliflozin, the median time to reach maximum plasma concentration (t_{max}) was approximately 1 to 2 hours. The mean terminal plasma elimination half-life ($t_{1/2}$) of canagliflozin was 10 and 13 hours with canagliflozin doses of 100 and 300 mg, respectively. The t_{max} was independent of dose. After repeated dosing with 50 to 300 mg canagliflozin, steady state was reached by 4 to 5 days. Minimal accumulation of canagliflozin was observed at steady-state across 50, 100, and 300 mg doses with mean accumulation ratios ranging from 1.3 to 1.4 in subjects with T2DM. Bioavailability of canagliflozin was not affected after co-administration of canagliflozin 300 mg with food in healthy subjects indicating that the canagliflozin tablet formulation may be taken without regard to meals.

O-glucuronidation is the major metabolic elimination pathway for canagliflozin in humans. In human plasma, 2 non-pharmacologically active *O*-glucuronide conjugates of unchanged drug, M5 (formed by UGT2B4) and M7 (formed by UGT1A9), were present. Co-administration with rifampin, a nonselective inducer of several UGT enzymes, decreased canagliflozin area under the curve (AUC) by 51%, which may decrease efficacy. There was an increase in the AUC and C_{max} of digoxin when co-administered with canagliflozin 300 mg. Subjects taking concomitant digoxin should be monitored appropriately. The C_{max} of canagliflozin was not meaningfully altered by renal impairment.

Based on in vitro data and the clinical drug-drug interaction studies conducted to date, the potential for clinically significant CYP450 based PK interactions appears to be low.

Pharmacodynamics

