Adverse drug reactions associated with canagliflozin include genital mycotic infections, urinary tract infections, adverse events related to osmotic diuresis, and adverse events related to reduced intravascular volume, as well as constipation, and a low incidence of rash or urticaria.

In men, the genital mycotic infections (including balanitis and balanoposthitis) occurred predominantly in uncircumcised individuals and in those with a past history of genital mycotic infections, generally did not lead to discontinuation from the study. Circumcision was performed in 17/3569 (0.5%) and 3/1924 (0.2%) of men treated with canagliflozin and control, respectively. In women, genital mycotic infections (including candidal vulvovaginitis) occurred more commonly in women with a prior history of genital mycotic infections and did not generally lead to discontinuation. A modest increase in the incidence of adverse events of urinary tract infection (mostly lower tract infections) was observed with canagliflozin relative to control, without an increase in serious adverse events of urinary tract infection.

Adverse drug reactions were observed that relate to the osmotic diuretic effect of canagliflozin, with increases in UGE leading to a diuretic action; this included ADRs of pollakiuria (increased urinary frequency), polyuria (increased urinary volume), and thirst. Adverse drug reactions related to reduced intravascular volume were observed including postural dizziness, orthostatic hypotension, and hypotension. Risk factors for volume-related adverse events on canagliflozin treatment were ≥ 75 years of age, eGFR of 30 to 60 ml/min/1.73m² and use of loop diuretics. These adverse events were generally considered as mild or moderate in intensity, and infrequently led to discontinuation. No increase in serious adverse events related to reduced intravascular volume were seen with canagliflozin treatment. The reduction in intravascular volume also led to reversible reductions in eGFR that generally attenuated with continued treatment.

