9.1.4. End-of-Treatment/Early Withdrawal

The end-of-treatment/early withdrawal evaluation will be performed when the double-blind treatment phase of the study is ended or at the time the subject is withdrawn from the study. The evaluation should be performed as soon as possible after stopping the study drug.

Refer to the Time and Events Schedule that follows the Synopsis for procedures at the End-of-Treatment/Early Withdrawal evaluation.

Subjects who prematurely discontinue double-blind treatment will have follow-up contact as described in Section 9.1.5, Posttreatment Phase (Follow-Up) and in the Posttreatment Time and Events Schedule. If it becomes no longer possible for a subject to continue to make site visits for posttreatment measurement of vital signs and laboratory specimen collection, the investigator may revert to telephone contacts (with the subject or, as a last resort, with relatives or a family physician) or other available medical records to assess and collect information regarding serious adverse events, CV events, and fractures on the timelines described in the Time and Events Schedule, and forego the clinic visits. Alternately, at the investigator's discretion, less frequent in-clinic visits may be interspersed with other forms of contact, including telephone, email, letters, social media sources, fax, or other electronic or non-electronic means.

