Urine samples from first morning void on day of designated visits will be collected for urine albumin and creatinine determinations. If the subject does not provide the morning void collection on the day of the visit, the subject may bring a first morning void specimen to the investigational site during the subsequent week. For subjects working a night shift, or who otherwise have atypical sleep patterns, the collection should be made at the end of the subject's usual sleep period.

The urine collections for exploratory analysis, as well as the routine urinalyses, should be obtained from a spot urine specimen in the clinic.

Urine glucose will not be measured in the first morning void urine specimens or urinalyses.

For SMBG monitoring during the study, see Section 6.2.1, Management of Glycemic Control and CV Risk Factors.

Vital Signs (pulse, blood pressure)

Vital signs will consist of pulse and blood pressure measurements and will be obtained after the subject has been in the sitting position for 5 minutes and before blood sample collection for laboratory tests. Pulse rate will be measured once at each clinic visit. Blood pressure will be assessed manually with a mercury sphygmomanometer, or a properly calibrated automated blood pressure monitor; if neither of these is available, a high-quality aneroid sphygmomanometer calibrated according to manufacturer specifications will be acceptable. Three consecutive blood pressure readings will be taken and recorded, at intervals of at least 1 minute apart, as specified in the Time and Events Schedule.

In addition, blood pressure will be measured 3 times in both arms at the screening visit; if there is a difference between arms of >10 mmHg in either the mean systolic or diastolic pressure, the arm with the higher pressure should be used to measure blood pressure and *should be used for all subsequent blood pressure measurements during the study*. If possible, if blood pressure is measured manually, it should be measured by the same individual, using the same equipment, at each clinic visit to reduce variability.

Body Weight

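### Section 11.4 applies the last-dose-plus-30-days window to laboratory values, vital signs and weight as well as adverse events, so drug-free values can be summarised with on-drug ones

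*Protocol*

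**What the plan says.** Section 11.4 states that "The safety analysis will be based on the mITT analysis set", and defines that set as randomized subjects who "have received at least one dose of study drug and their data occurring between first dose and last dose plus 30 days". The comparisons it then lists include "clinically important changes in clinical laboratory tests, vital signs (pulse, blood pressure), and body weight between randomized groups". The 30-day limit is repeated for treatment-emergent adverse events. No shorter window is given for measurements.

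On the drug, Section 1.1.2 reports that the mean terminal half-life "of canagliflozin was 10 and 13 hours with canagliflozin doses of 100 and 300 mg, respectively". In its safety summary it says: "The reduction in intravascular volume also led to reversible reductions in eGFR".

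On visit timing, Section 9.1.4 says of the end-of-treatment/early-withdrawal assessment: "The evaluation should be performed as soon as possible after stopping the study drug". Footnote b of the Time and Events Schedule agrees: "Evaluations will be performed as soon as possible after stopping the study drug". Neither sets a maximum number of days. For urine, Section 9.4 allows that, when the void is not provided on the visit day, "the subject may bring a first morning void specimen to the investigational site during the subsequent week". Footnote p of the schedule repeats this. Neither place makes an exception for the end-of-treatment visit.

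**The concern.** A 30-day tail is a sensible convention for adverse events, which may surface or be reported some time after exposure. A laboratory value or blood pressure is different: it describes the subject on the day it is taken. If the effect on that measure reverses when drug stops, a value from well after the last dose describes an untreated subject, whichever arm the subject was in.

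Under Section 11.4 such a value belongs to the same data set as the on-drug values. Mean changes that include it move toward no difference between arms. For a safety measure, that understates an effect of the drug. If the arms stop drug at different rates, the share of drug-free values also differs by arm. Section 1.1.2 reports slightly more discontinuations for adverse events on canagliflozin than on control, so this is plausible, but the protocol does not let one quantify it.

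**Working it through.** The protocol gives no washout time or measurement window, so there is no figure of its own to reproduce. The check sets the half-life against the windows.

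**Inputs**
- Half-life h: 10 hours (100 mg) and 13 hours (300 mg), Section 1.1.2.
- Safety data window: 30 days after last dose, Section 11.4.
- Late-urine allowance: up to 7 days after the visit, Section 9.4 and footnote p.
- Assumptions: first-order elimination, with washout taken as five half-lives.

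**Formulas**
- Half-lives elapsed at time t = t / h.
- Fraction of drug remaining = 2^(−t/h).

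**Results**

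| Time after last dose | h = 10 hours | h = 13 hours |
|---|---|---|
| Five half-lives | 50 hours = 2.1 days | 65 hours = 2.7 days |
| 3 days (72 hours) | 7.2 half-lives, 0.7% left | 5.5 half-lives, 2.2% left |
| 7 days (168 hours) | 16.8 half-lives, 0.0009% left | 12.9 half-lives, 0.013% left |
| 30 days (720 hours) | 72 half-lives | 55 half-lives |

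Share of the 30-day tail lying beyond five half-lives: 1 − 2.08/30 = 93% and 1 − 2.71/30 = 91%. This is a share of calendar time, not of measurements.

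**What falls in the tail.** The follow-up contact about 30 days after the last dose is by default a telephone call, and Section 9.1.5 lists only events to be collected at it. The Posttreatment Time and Events Schedule starts after that contact. For subjects still on drug at study end, Section 3.1 plans last on-treatment visits separately from the 30-day off-drug visit. The measurements that can fall in the tail are therefore mainly:
- early-withdrawal visits held some days after stopping;
- optional or unscheduled visits;
- make-up urine samples.

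**Effect on a difference.** If a share f of the values in a summary is drug-free in each arm and the effect has fully reversed, the observed difference is (1 − f) times the on-drug difference. The protocol gives neither f nor the speed of reversal for any measure.

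**The case against.** Four objections have weight.

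*Measurement windows are usually SAP detail.* Section 11 does leave specifics to the SAP. But Section 11.4 does not leave this window open: it fixes 30 days for the set on which all safety data are analysed. Section 11.1 defers only the alignment of secondary endpoints with the analysis sets, and Section 11.4 defers the criteria for markedly abnormal laboratory values. If the SAP narrows the window, the protocol text should agree with it. It is also true that the protocol uses the term treatment-emergent only for adverse events.

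*Few measurements fall in the tail.* This stands. Descriptive summaries are also by scheduled time point, so routine on-drug visits are untouched.

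*Plasma clearance is not loss of effect.* This stands too. The protocol gives no offset time for blood pressure, weight, creatinine or any other measure. It calls the eGFR reductions reversible and says they generally attenuated with continued treatment, but gives no time course after stopping.

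*A short window could hide toxicity.* A subject who stopped for an abnormality and was seen a few days later could drop out of the main table. Replacing that value with an earlier one would also conflict with the rule in Section 11.4 against imputing missing laboratory and vital-sign values. Any change has to meet both points.

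A reader might also infer that the gatekept albuminuria endpoint is biased by late urine. The protocol does not support that. Albumin/creatinine ratio, albuminuria progression and HOMA-B are efficacy endpoints outside Section 11.4, and their analysis set is expressly left to the SAP. The protocol deliberately collects albumin/creatinine ratio after discontinuation, and under an intent-to-treat analysis off-drug values may belong in the comparison. For these endpoints the urine point concerns only when the sample was taken and how it is labelled.

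**Conclusion.** The point holds as a poorly fitted rule of moderate reach. One window is applied to events and to measurements, although drug is essentially gone within about 3 days, and nothing in the visit or urine rules keeps later values apart. The likely direction for mean changes in reversible measures is toward no difference. For percentages of subjects with abnormal values, the direction depends on a detail that the protocol does not state. If any value in the window counts, off-drug values can only add subjects.

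The size cannot be computed from the protocol. A reader might try: 5% annual dropout (Section 11.3) over an assumed 6 years gives 1 − 0.95^6 = 26% with an early-withdrawal visit. If 25% to 100% of those visits were late, 7% to 26% of end-of-treatment values would be drug-free. The documents do not support that range. The 5% is a planning dropout rate, not a rate of stopping drug, and subjects lost to follow-up may have no such visit. The share of late visits has no source, and 100% sits badly with the instruction to hold the visit as soon as possible. Full reversal is assumed throughout.

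The conclusion rests on first-order elimination, on five half-lives as washout, and on some safety measures reverting off drug.

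**What to change.** - **Adverse events:** keep last dose plus 30 days.
- **Laboratory, vital-sign and weight summaries:** in Section 11.4, define an on-treatment window of a few days after the last dose, justified by the half-life. Do not carry earlier values forward.
- **Later values:** report those from the end of that window to day 30 in a separate off-drug table, including markedly abnormal results, so that abnormalities in subjects who stopped for toxicity stay visible.
- **Urine at the end-of-treatment visit:** in Section 9.4 and footnote p, ask that the first morning void be collected on or before the visit day, while the subject is still on drug where possible. Flag make-up samples as off-drug. This concerns sampling and labelling only, not when drug is stopped.
- **Albumin/creatinine ratio, albuminuria progression and HOMA-B:** leave the choice between intent-to-treat and on-treatment analysis to the SAP.

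The cost is a date filter in programming, one sentence to sites and one additional table. The on-treatment tables will hold slightly fewer values.
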